### 10.2 Datasets to be analyzed

All analyses will be based on mITT population defined as below.

Modified Intent-to-treat (mITT) population: The mITT population will be defined as all subjects randomized into the trial who received at least one dose of lenalidomide. Treatment classification will be based on the randomized treatment.

Patients who did not receive any treatment of lenalidomide will not be included in the statistical analysis. Patients who have received at least one dose of lenalidomide will be considered evaluable for statistical analysis.

### 10.3 Statistical Methodology

Each treatment arm will be further stratified into those patients who received a reduction in dosage level and those who did not. As a first step, potential differences among the four groups on demographic variables will be tested. Those variables that are categorical will be analyzed by Chi Sq.; those variables that are quantitative will be analyzed by two-way between-groups Analyses of Variance. Any variable where a significant difference is established will be controlled by entry into future analyses as covariates.

The primary outcome variable is the proportion of patients in each treatment arm that received any dosage reduction, independent of when in the course of treatment this reduction occurred or how many subsequent reductions were introduced. These data will be analyzed by logistic regression with treatment arm as the main predictor and any variables found significant in the first step entered as covariates. A secondary analysis will consider the rate at which any dose reductions were introduced. For example, it is possible that the proportion of patients that receive a dose reduction may be equivalent in the two treatment arms, but that those patients in one arm may have received their reductions earlier. This will be examined by a Cox Proportional Hazard test, and, if necessary, with the same covariates identified above.

Power analysis shows that with a total N = 80 (40/group) power = .80 to detect an effect size difference in proportions of 32% (p=.05, 2-tail) (Borenstein M, Rothstein H and Cohen J. Power and Precision (2004). Englewood, NJ, Biostat).

This sample size provides adequate power to observe similar difference in dose reduction between the two groups for a range of dose reductions (10% - 40%) in 15mg dose group.

**Secondary endpoints:** Although this study is not powered to compare response as well as duration of response to the 2 dose regimen, we will collect and analyze both using power analysis. Objective response rate is defined as the proportion of randomized subjects who have evidence of either partial response or complete response as determined using the EBMT and IMWG criteria. One-sided 95% confidence limits on the lower limit of the percentage of responders will be established to determine if this lower bound exceeds 45%. Duration of response is computed among the subgroup of subjects whose best response is PR or better. It is defined as is the time from when measurement criteria are first met for objective response until the date of progression or death. A subject with an objective response who does not have a progression event will be censored at the same time as he or she was censored under the primary definition of PFS.

The data on growth factors and other markers will be collected. For each protein, the proportion of patients who are up or down-regulated will be reported along with the 90% CI. The Fisher's exact test (two sided significance level of 5%) will be used to compare the proportions of patients with CR+PR for those who are upregulated vs. those who are down-regulated.

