### 3.3 Rationale

The primary rationale is to utilize Revlimid at dose that will be well tolerated and effective. We propose to use the need for dose reduction as a criterion to judge tolerability from various causes. In the veteran population which predominantly is in the older age category with number of co-morbidities, a lower dose regimen may be safer and advantageous. In a recent multi-institutional study, the 009 and 010 studies, patients were randomized to receive Revlimid with dexamethasone versus dexamethasone alone. A logistic regression was performed using dose reduction (i.e., whether or not having any lenalidomide dose reduction as the dependent variable). Treatment-emergent neutropenia and thrombocytopenia were the causes of the majority of dose reductions. Predictors analyzed included: age, prior transplant (yes vs. no), high vs. low risk (disease stage variable), previous thalidomide exposure (yes vs. no), previous lines of therapy (<=2 vs. 3+), prior medical history of neutropenia or thrombocytopenia. Among the 353 patients in the Revlimid/Dexamethasone groups, 131 (37.1%) had at least one dose reduction of Revlimid. Age, whether used as a continuous variable or dichotomized one (<=65 vs. 66+), was the single significant predictor for dose reduction; 46% of the patients aged 66 or older required at least one dose reduction, as compared to 31% of the patients aged 65 or younger. Of

interest, when the elderly population was specifically examined, the outcomes were similar for response rate, time to progression and overall survival than the younger group, suggesting that dose reduction had no significant effect on efficacy.

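### Section 10.3 selects the primary model's covariates by tests on groups defined partly by the primary outcome, so the odds ratio to be estimated is not settled until outcomes are known

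*Combined protocol and SAP*

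**What the plan says.** Section 10.3 (Statistical Methodology) sets out these steps in order.

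- Grouping: "Each treatment arm will be further stratified into those patients who received a reduction in dosage level and those who did not". This gives four groups, arm by dose reduction (yes or no).
- Screening: "potential differences among the four groups on demographic variables will be tested". Categorical variables get a chi-square test; for the rest, "those variables that are quantitative will be analyzed by two-way between-groups Analyses of Variance".
- Selection: "Any variable where a significant difference is established will be controlled by entry into future analyses as covariates".
- Outcome: "The primary outcome variable is the proportion of patients in each treatment arm that received any dosage reduction", whatever the timing or number of reductions.
- Primary model: logistic regression with arm as main predictor and "any variables found significant in the first step entered as covariates".
- Secondary Cox model for time to reduction: adjusted "if necessary, with the same covariates identified above".

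The section does not list the demographic variables, give the screening significance level, or say which ANOVA effect counts as a significant difference. No other section fixes a covariate set. Section 3.3 reports that in the two earlier phase III trials age "was the single significant predictor for dose reduction", with 46% of patients aged 66 or older needing a reduction against 31% of younger patients. Section 10.1 says the results should help choose a dose for elderly patients.

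**The concern.** A check of baseline balance compares randomised arms and uses no outcome data. This screen does use outcome data: half of the grouping is the variable that the primary model then explains. A covariate can enter because it happens to be associated with dose reduction in this sample.

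This matters for the estimate more than for the test. If there is no treatment effect, the odds ratio for arm is 1 whichever baseline variables are in the model. If there is an effect, the logistic odds ratio depends on the covariates conditioned on, even under perfect randomisation. The quantity being estimated is therefore not settled until outcomes are in, and it can change from one sample to the next.

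The rule also leaves room for the analyst. A two-way ANOVA yields three F-tests (arm, reduction, interaction), whereas a difference among four groups can also be read as one overall 3-df test. Two careful statisticians could fit different primary models to the same data. The Cox analysis inherits the choice.

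**Working it through.** **1. The plan's own power figure.** Section 10.5 gives 50% and 20%, 40 per arm and a 0.05 level; Section 10.3 says two-tailed. With pooled variance under the null (mean rate 0.35):

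Power = Φ[(0.30 − 1.96·√(2·0.35·0.65/40)) / √((0.5·0.5 + 0.2·0.8)/40)] = Φ[(0.30 − 1.96·0.1067)/0.1012] = Φ(0.898) = 0.8155.

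The stated 81.6% is reproduced. It refers to the unadjusted comparison.

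**2. Chance entry of irrelevant variables.** The number of candidates and the 0.05 screening level are assumptions. With m independent tests, P(at least one enters) = 1 − 0.95^m. The low reading uses one test per variable; the high reading lets any of three F-tests admit a quantitative variable. Simulated figures come from 40,000 trials per scenario, 40 per arm, with 35% reductions in both arms.

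| Candidates (quantitative + binary) | m, low / high | Formula | Simulated |
|---|---|---|---|
| 3 (1+2) | 3 / 5 | 14.3% / 22.6% | 14.3% / 22.3% |
| 4 (2+2) | 4 / 8 | 18.5% / 33.7% | 18.6% / 33.0% |
| 8 (3+5) | 8 / 14 | 33.7% / 51.2% | 33.6% / 50.4% |

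Three candidates is the case to lead with, since the screen is limited to demographic variables.

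**3. Assumed age effect.** From Section 3.3: ln(0.46/0.54) − ln(0.31/0.69) = −0.160 + 0.800 = 0.640. The two halves of a normal distribution lie 1.596 SD apart, so the slope is 0.640/1.596 = 0.40 per SD. This assumes a cut near the median age. The age spread in this trial is not given.

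**4. Two readings of the ANOVA rule** (three candidates, age slope 0.40, rates 50% and 20%).

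- Age enters in 22% of trials under the overall test and 38% under any-of-three.
- The covariate sets differ in 18.8% of trials.
- When they differ, the two odds ratios from the same data differ by a median factor of 1.11, with a 90th percentile of 1.29.
- Over all trials, a factor of 1.28 or more occurs in about 0.188 × 0.10 ≈ 2%. A separate run of 4,000 trials per scenario also gave about 2%, and 0.2% at 35% in both arms.
- In that run the significance verdict differed between readings in under 1% of trials.

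For scale, the unadjusted log odds ratio at 20/40 versus 8/40 has SE √(1/20 + 1/20 + 1/8 + 1/32) = 0.506. A factor of 1.11 is ln 1.11 = 0.104, about one-fifth of an SE; a factor of 1.28 is 0.247, about half an SE.

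**5. Error rates and standard error** (three candidates, age slope 0.40, 40,000 trials). Type I error and SE ratio are at 35% in both arms; power is at 50% versus 20%.

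| | Overall test | Any of three | Unadjusted | Age fixed |
|---|---|---|---|---|
| Type I error | 5.0% | 5.1% | 4.7–5.0%* | 4.8–5.1%* |
| Power | 0.820 | 0.823 | 0.816 | 0.825 |
| Mean SE / empirical SD | 0.970 | 0.966 | 0.984 | 0.974 |

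*Range over all null scenarios run. Over the same scenarios, with up to eight candidates, the plan's type I error was 5.0–5.4%. Simulation error is about 1.96·√(0.05·0.95/40,000) = 0.2 points.

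Against fixed age, the SE ratio is lower by 0.4 to 0.8 points. The largest gap is 2.7 points (0.951 against 0.978), with eight candidates and any-of-three. In the 4,000-trial run, a model with all three candidates fixed in advance, and so no selection, had a ratio of 0.961, below the plan's 0.970–0.973.

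**The case against.** The case for leaving the text alone is fair. The rule is written down before the data, the trial is phase II, randomisation protects the arm comparison, and the error rates hardly change. The demographic list is probably short. A two-way ANOVA most naturally means separate effect tests, which narrows the ambiguity. The large odds-ratio discrepancies are rare once counted over all trials.

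Most of this stands, and it rules out three stronger readings that a reader might infer.

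- **Alpha inflation.** Selecting covariates with sight of the outcome suggests a biased test. The simulations do not show one of any consequence: type I error is at most 5.4% across the scenarios, and 5.0–5.2% with three candidates.
- **A standard error made materially too short by selection.** The ratio does fall below 1, but it does so without selection too, and a larger model fixed in advance does worse. Most of the shortfall is ordinary small-sample behaviour of logistic regression with added covariates.
- **Harm from leaving age out.** Age will often fail the screen, but an unadjusted primary analysis would be acceptable and omits age every time, with power 0.816 against 0.825. Omission is not in itself an error; having the outcome data decide it is the problem.

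The objection does not answer the central point. A rule fixed in advance is not a model fixed in advance when one of its inputs is the primary outcome and its trigger is undefined.

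**Conclusion.** The concern holds as a fault of pre-specification. As Section 10.3 stands, the primary odds ratio depends on outcome-driven selection and on an unstated reading of the ANOVA rule. Its practical size is modest: with three candidates, an irrelevant variable enters in about 14–22% of noise-only trials; the two readings choose different covariates in about 19% of trials and give odds ratios differing by a factor of 1.28 or more in about 2%; the significance verdict changes in under 1%. Type I error and power of about 0.82 are essentially unaffected.

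That the screen uses the outcome and that no covariate is named follow directly from the text. The percentages rest on assumptions the documents do not supply: three candidates (one quantitative, two binary), screening at 0.05, and an age slope of 0.40 per SD. A longer candidate list raises the selection rates, as the first table shows. The point is still worth acting on, because the estimate and its interval will inform the choice of dose and the correction is nearly free.

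**What to change.** In Section 10.3, remove the four-group screen as a selection step and name one primary model in advance. The preferred choice is logistic regression of any dose reduction on arm and continuous age. Age is known for every patient from the eligibility check, and Section 3.3 supports it as a predictor. Report the unadjusted difference in proportions with a 95% CI alongside. Naming the unadjusted comparison as primary would also settle the matter.

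Use the same fixed covariate in the Cox model in place of the conditional wording. Show baseline variables descriptively by randomised arm, without tests.

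The cost is one rewritten paragraph, with no new data and no extra patients. N = 80 and the stated 81.6% can stay; simulated power with age fixed is 0.825 in the three-candidate scenario.

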##### **5.1.1.3 Pharmacokinetics and Drug Metabolism:**

##### **Absorption:**

Lenalidomide, in healthy volunteers, is rapidly absorbed following oral administration with maximum plasma concentrations occurring between 0.625 and 1.5 hours post-dose. Co-administration with food does not alter the extent of absorption (AUC) but does reduce the maximal plasma concentration (Cmax) by 36%. The pharmacokinetic disposition of lenalidomide is linear. Cmax and AUC increase proportionately with increases in dose. Multiple dosing at the recommended dose-regimen does not result in drug accumulation.

Pharmacokinetic sampling in myelodysplastic syndrome (MDS) patients was not performed. In multiple myeloma patients maximum plasma concentrations occurred between 0.5 and 4.0 hours post-dose both on Days 1 and 28. AUC and Cmax values increase proportionally with dose following single and multiple doses. Exposure (AUC) in multiple myeloma patients is 57% higher than in healthy male volunteers.

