##### **Metabolism and Excretion:**

The metabolic profile of lenalidomide in humans has not been studied. In healthy volunteers, approximately two-thirds of lenalidomide is eliminated unchanged

through urinary excretion. The process exceeds the glomerular filtration rate and therefore is partially or entirely active. Half-life of elimination is approximately 3 hours.

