## **5.2.2 Exclusion criteria**

**5.2.2.1** Any serious medical condition, laboratory abnormality, or psychiatric illness that would prevent the subject from signing the informed consent form.

**5.2.2.2** Pregnant or breast feeding females. (Lactating females must agree not to breast feed while taking lenalidomide).

**5.2.2.3** Any condition, including the presence of laboratory abnormalities, which places the subject at unacceptable risk if he/she were to participate in the study or confounds the ability to interpret data from the study.

**5.2.2.4** Renal insufficiency of creatinine clearance < 40 mL/min

**5.2.2.5** Known hypersensitivity to thalidomide or lenalidomide.

**5.2.2.6** The development of erythema nodosum if characterized by a desquamating rash while taking thalidomide or similar drugs.

**5.2.2.7** Concurrent use of other anti-cancer agents or treatments.

**5.2.2.8** Known seropositive for an active viral infection with human immunodeficiency virus (HIV), hepatitis B virus (HBV) or hepatitis C virus (HCV). Patients who are seropositive because of hepatitis B virus vaccine are eligible.

**5.2.2.9** Subjects with hemoglobin < 8.0 g/dL. The use of transfusion with pRBC to correct anemia and meet eligibility criteria will not be allowed.

**5.2.2.10** Patient has an absolute neutrophil count <  $1.0 \times 10^9/L$  within 14 days before enrollment

**5.2.2.11** Peripheral neuropathy of grade 3 or greater. Patients with painful grade 2 neuropathy are also excluded.

**5.2.2.12** Patient has platelet count <  $75 \times 10^9/L$  within 14 days before enrollment.

**5.2.2.13** Plasma cell leukemia at time of study entry.

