#### **10.5 Sample size and power considerations**

Assume the dose reduction rate for 25 mg arm is 50%, a sample size of 80 subjects (40 per arm) will provide a power of 81.6% to detect a difference of 30% (the rate of dose reduction assumed to be 20%) at significance level of 0.05.

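### Screening creatinine clearance, already collected and plausibly prognostic for dose reduction, lies outside the stated covariate pool for the primary logistic and Cox models

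*Combined protocol and SAP*

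**What the plan says.** The primary outcome in section 10.3 is the proportion of patients in each arm with any lenalidomide dose reduction. It is analysed by logistic regression on treatment arm plus covariates, and a Cox model for the timing of reductions uses the same covariates if needed. Candidates come from a first step in which "potential differences among the four groups on demographic variables will be tested"; the four groups are the two arms, each split by whether the dose was reduced. No list of variables is given. Creatinine clearance is not named in section 10, and no stratification of the randomisation by renal function is described.

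Four other places bear on this:

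- Section 5.1.1.3, Metabolism and Excretion: "In healthy volunteers, approximately two-thirds of lenalidomide is eliminated unchanged" in urine. The same paragraph says that this excretion exceeds glomerular filtration and is at least partly active.
- Section 5.1.1.3, Absorption: "AUC increase proportionately with increases in dose". Proportionality is stated for myeloma patients too.
- Section 5.2.2: the only renal limit is exclusion for "Renal insufficiency of creatinine clearance < 40 mL/min". Section 5.4.1 gives everyone who qualifies one of the same two starting regimens.
- Section 2: creatinine clearance is in the serum chemistry panel at screening and at later visits.

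The stated setting is a dose for older patients. Section 3.3 opens its argument with "In the veteran population which predominantly is in the older age category with number of co-morbidities".

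**The concern.** The trial compares two levels of exposure to one drug. If exposure also varies with renal function within each arm, clearance is a natural predictor of the primary event. The protocol supports each link. Elimination is largely renal, AUC follows dose, and low neutrophil and platelet counts were dose-limiting (section 3.2). Neutropenia and thrombocytopenia caused most dose reductions in the 009 and 010 studies (section 3.3).

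A baseline variable of this kind would normally be fixed in the model in advance. Here it is outside the stated pool, whatever the first step finds. Two things are at stake. One is some protection of the estimate against chance imbalance in renal function. The other is interpretation, because one rate per arm averages over patients whose risks may differ widely. How covariates are selected in the first step is a separate matter. The point here is which variable is missing.

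**Working it through.** **1. The plan's own power figure.** Section 10.5 assumes 50% on 25 mg and 20% on 15 mg, with 40 per arm and alpha 0.05. With pooled variance under the null and a two-sided test:

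z = [0.30 × √40 − 1.96 × √(2 × 0.35 × 0.65)] / √(0.25 + 0.16) = (1.897 − 1.322) / 0.640 = 0.90

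Power is 81.55%, which reproduces the stated 81.6%. No figure in the plan is wrong on this point. Expected events are 0.50 × 40 + 0.20 × 40 = 20 + 8 = 28.

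**2. Exposure against clearance.** Inputs from the documents are a renal share of about 2/3, AUC proportional to dose, and a floor of 40 mL/min. Assumptions are that renal elimination is linear in creatinine clearance, that the healthy-volunteer share carries over to patients, and a reference clearance, for which the documents give no value. Then

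AUC ratio = 1 / [1/3 + (2/3) × 40 / reference]

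| Reference (mL/min) | 60 | 70 | 80 | 90 | 100 | 110 | 120 |
|---|---|---|---|---|---|---|---|
| AUC at 40 relative to reference | 1.29 | 1.40 | 1.50 | 1.59 | 1.67 | 1.74 | 1.80 |

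The dose contrast is 25/15 = 1.67, matched only at a reference of 100. Over the same references the ratio runs from 1.25 to 1.67 with a renal share of 0.60, and from 1.30 to 1.88 with a share of 0.70.

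**3. What that would mean for risk.** Assume that the logit of risk is linear in log exposure, with the slope chosen so that the marginal rates are 50% and 20%, and that clearance is uniform on 40 to 100 mL/min. Between 40 and 100 mL/min, risk then falls from 69% to 34% on 25 mg and from 34% to 11% on 15 mg.

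**4. Effect of chance imbalance.** In that scenario the SD of clearance is 60/√12 = 17.3 mL/min. The SD of the difference in arm means is 17.3 × √(2/40) = 3.9 mL/min. Average risk slopes are (69 − 34)/6 = 5.8 and (34 − 11)/6 = 3.8 points per 10 mL/min, mean 4.8. Other assumed distributions give 3.9 to 5.2. A one-SD imbalance therefore moves the crude difference by about 0.39 × 4.8 = 1.9 points. The standard error of that difference is √(0.25/40 + 0.16/40) = 10.1 points. The share of variance is about (1.9/10.1)² = 3.5%.

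**5. Power with and without adjustment.** Each scenario simulates 3,000 trials of 40 per arm under the model in step 3. The covariate is the exposure term computed from clearance, so its functional form is correct by construction.

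| Clearance, uniform (mL/min) | Unadjusted | Adjusted |
|---|---|---|
| 40–80 | 82.7% | 82.9% |
| 40–100 | 81.7% | 81.9% |
| 40–120 | 80.9% | 82.9% |

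The Monte Carlo standard error is about 0.7 points per entry. Bell-shaped clearance distributions (mean/SD 70/22, 80/25 and 65/15 mL/min) gave 83.7% vs 84.5%, 82.4% vs 83.8% and 83.6% vs 84.1%. The gain is about 0 to 2 points throughout.

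**The case against.** The strongest reply is that nothing is broken. Allocation is randomised 1:1, so imbalance in clearance is equally likely in either direction and is already covered by the error rate and interval of the unadjusted analysis. A reader might infer that omitting clearance lets renal function pass for a dose effect. The documents and the arithmetic do not support that: a typical imbalance is worth about 2 points against a standard error of about 10. This part of the objection stands.

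A reader might also infer that, on the protocol's own figures, renal function changes exposure as much as the dose contrast does. That is not supported either. The protocol gives no comparison clearance, no distribution and no relation between clearance and exposure. Its statement that excretion is partly or wholly active makes linear scaling an assumption. For references of 60 to 90 mL/min the ratio is 1.29 to 1.59, short of 1.67. The risks in step 3 are not evidence: their slope is solved from the planning rates and then carried over to differences between patients.

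Nor is clearance expressly excluded. It is unnamed, and the pool is undefined. Age, the one significant predictor in the 009/010 analysis (46% vs 31%), is already a candidate. That analysis lists no renal variable, however, so it neither supports nor refutes clearance, and age enters here only if it passes the first step.

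Finally, adjustment has a cost in interpretation. The adjusted odds ratio is conditional, whereas the planned outcome is a proportion per arm. That is correct, and the fix has to deal with it.

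**Conclusion.** The gap is real but small. Read literally, section 10.3 offers no route into the primary or Cox model for a baseline value that is already collected and that the protocol's pharmacology makes plausibly prognostic. The unadjusted comparison remains valid, the stated power reproduces, and adjustment would add about 0 to 2 points of power. The case for the change rests on modest protection against imbalance and on a clearer estimate for an older population.

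The exposure range of about 1.3 to 1.8 rests on linear scaling, a two-thirds renal share in patients and a reference of 60 to 120 mL/min. The risk and power figures rest further on risk following exposure at the slope implied by 50% vs 20%. This is an inexpensive improvement to the analysis plan, not the correction of an error.

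**What to change.** In section 10.3:

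- Name log screening creatinine clearance as a fixed, continuous covariate in the logistic and Cox models, regardless of its p-value and of the first step. State how clearance is obtained, since the schedule does not say.
- Report the crude dose-reduction proportions per arm together with the covariate-standardised (marginal) proportions and risk difference from the logistic model. State that the adjusted odds ratio is conditional and is not interchangeable with the crude one.
- Label any model-based proportions at particular clearance values as exploratory. With about 28 events they will be imprecise.

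The cost is a few sentences and one degree of freedom. No new data, visit, dose or eligibility change is involved.

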## 2 Schedule of Study Assessments \*

Procedure	Screening ≤ 14 days from Baseline (First day study drug administration)	Cycle 1				 Cycles 2, 4, 6, 8+	 Cycles 3, 5, 7, 9+	Discontinuation From Study Drug
		Day 1	Day 8	Day 15	Day 22	Day 1	Day 1	
Record prior medications, treatments	X							
Record prior anti-cancer therapies	X							
Physical examination, vital signs	X	X				X	X	X
Weight	X							
ECOG performance status	X							
Chest x-ray 	X 							X 
ECG	X							
Register patient for RevAssist® 	X							
Pregnancy testing 	X 	X	X	X	X	X 	X 	X 
Education and counseling checklist 	X 	X 				X 	X 	
Skeletal Survey	X							X
Hematology • CBC, differential, platelets	X	X	X	X	X	X	X	X
Serum chemistry • Electrolytes, BUN, glucose, creatinine • Liver profile : SGOT, SGPT, alkaline phosphatase, total bilirubin, total protein, albumin • Calcium • CrCl ≥ 40 ml/min • Amylase ≤ 2.5x upper limit of normal	X X X X X	X X X X X	X X X X X	X X X X X	X X X X X	X X X X X	X X X X X	X X X X X
Multiple Myeloma Disease Assessment: • β 2 -microglobulin, C-reactive protein  • Serum protein electrophoresis with quantitated M-protein and Freelite	X  X					X	X	X
Serum Secretors: • Quantitative immunoglobulins • Serum immunofixation	X X					X X	X X	X X
Urine Secretors: • 24hr Urine total protein and urine protein electrophoresis and urine freelite • Immunofixation from 24hr urine	X  X 					X  X 	X  X 	X  X 

Procedure	Screening ≤ 14 days from Baseline (First day study drug administration)	Cycle 1				 Cycles 2, 4, 6, 8+	 Cycles 3, 5, 7, 9+	Discontinuation From Study Drug
		Day 1	Day 8	Day 15	Day 22	Day 1	Day 1	
Non-secretors: • Freelite™ • Bidimensional measurement of soft tissue plasmacytomas if present 	X X					X X 	X X 	X X 
Bone marrow aspirate and biopsy • Cytogenetics  • Morphology	X  X							X 
HIV Test	X							
Hep A,B,C titers (HAV, HBV, HCV)	X							
Dispense Cycle 1 study drug		X						
Response assessment 						X 	X 	X
Record adverse events		X	X	X	X	X	X	X
Record concomitant meds/procedures		X				X	X	X

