### 5.5.2 Instructions for initiation of a New Cycle

A new course of treatment may begin on the scheduled Day 1 of a new cycle if:

- The ANC is  $\geq 1000/\text{mm}^3$
- The platelet count is  $\geq 50000/\text{mm}^3$
- Any drug-related rash, allergic reaction/hypersensitivity or sinus bradycardia/ other cardiac arrhythmia adverse event that may have occurred has resolved to  $\leq$  grade 1 severity;
- Any other drug-related adverse events that may have occurred have resolved to  $\leq$  grade 2 severity.

If these conditions are not met on Day 1 of a new cycle, the subject will be evaluated weekly and a new cycle of treatment will not be initiated until the toxicity has resolved as described above. If lenalidomide dosing was halted during the previous cycle and was restarted with a one-level dose reduction without requiring an interruption for the remainder of the cycle, then that reduced dose level will be initiated on Day 1 of the new cycle. If lenalidomide dosing was omitted for the remainder of the previous cycle or if the new cycle is delayed due to toxicity newly encountered on the scheduled Day 1, then the new cycle will be started with a one-level dose reduction of lenalidomide. Treatment may be delayed upto 21 days from the original schedule but patients must follow the schedule for subsequent cycles.

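### Section 10.3 gives pre-treatment neutrophil and platelet counts no stated route into the primary model, so a possible power gain of unknown size is forgone

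*Combined protocol and SAP*

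**What the plan says.** **Covariate rule (10.3).** Each arm is split into patients with and without a dose reduction, and "potential differences among the four groups on demographic variables will be tested". Variables with a significant difference become covariates in later analyses, including the primary logistic regression of any reduction on arm and, if necessary, the Cox model for time to reduction. No list of variables is given.

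**Cause of the endpoint (3.3).** In the two earlier trials, "Treatment-emergent neutropenia and thrombocytopenia were the causes of the majority of dose reductions". Of the predictors tested there, including prior history of neutropenia or thrombocytopenia, only age was significant.

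**Entry limits and dosing rules.** Section 5.2.2 excludes a patient when "Patient has an absolute neutrophil count" applies with a value below 1.0 × 10⁹/L, or when platelets are below 75 × 10⁹/L. Section 5.5.2 requires ANC of at least 1000/mm³ and platelets of at least 50,000/mm³ to start a cycle. If the start is delayed for toxicity first met on the scheduled Day 1, "then the new cycle will be started with a one-level dose reduction of lenalidomide".

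**Data collected (Section 2).** "CBC, differential, platelets" is scheduled at screening and at Cycle 1 Day 1.

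**Power (10.5).** "Assume the dose reduction rate for 25 mg arm is 50"%, with "the rate of dose reduction assumed to be 20"% in the 15 mg arm; "a sample size of 80 subjects (40 per arm) will provide a power of 81.6"%.

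**The concern.** The primary event is any lenalidomide reduction, and the protocol attributes most reductions in the earlier trials to falls in two blood counts. The starting level of those counts is a natural candidate predictor, and it is measured before treatment in every patient. Section 10.3 nevertheless offers one source of covariates, an undefined demographic set, and does not name the counts.

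The way in is also poorly specified. Two of the four screening groups differ from the other two only by the outcome, so the outcome data help decide which covariates enter the primary model. In an open-label trial, that leaves the form of the primary model to be settled after the results can be seen.

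At stake is some efficiency in a trial planned at about 80% power with no stated dropout allowance, and a primary model that could have been fixed in advance.

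**Working it through.** **1. The plan's figure.** Inputs from 10.5 and 10.3: 40 per arm, rates 0.50 and 0.20, two-sided 0.05.

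- Pooled rate: (0.50 + 0.20)/2 = 0.35
- Standard error under no difference: √(2 × 0.35 × 0.65/40) = 0.1067
- Standard error under the alternative: √((0.50 × 0.50 + 0.20 × 0.80)/40) = 0.1012
- Power: Φ((0.30 − 1.96 × 0.1067)/0.1012) = Φ(0.90), or 81.55% unrounded

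This reproduces 81.6%. No covariate enters the calculation, so leaving the counts out takes nothing from it.

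**2. Link to the endpoint.** The ANC entry limit of 1.0 × 10⁹/L equals 1000/mm³, the new-cycle floor, so the margin at the limit is zero. For platelets it is 75,000 − 50,000 = 25,000/mm³. This shows a mechanism. It does not show how strongly counts predict reductions across the patients enrolled.

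**3. What adjustment could add.** The model is logit P(reduction) = a(arm) + βx. Here x is a standardised count signed so that higher x means more risk, and β = ln(OR per SD). Intercepts are set so that the arm rates stay at 20% and 50%. With two counts the term is β(x₁ + x₂) with correlation 0.3, so its SD is β√(2 + 2 × 0.3) = 1.61β. The ORs and the correlation are assumptions. Results are Wald-test power at 40 per arm, with 6,000 runs per case for one count and 5,000 for two (Monte Carlo error about √(0.82 × 0.18/5000) = 0.5 points).

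| Assumed OR per SD | One count: unadjusted → adjusted | Gain (points) | Both counts: unadjusted → adjusted | Gain (points) |
|---|---|---|---|---|
| 1.0 | 81.3% → 81.3% | 0.0 | 81.1% → 80.9% | −0.2 |
| 1.5 | 81.7% → 82.6% | 0.9 | 81.3% → 84.4% | 3.1 |
| 2.0 | 81.4% → 84.2% | 2.8 | 81.2% → 88.0% | 6.8 |
| 3.0 | 82.3% → 88.4% | 6.1 | 82.5% → 93.3% | 10.8 |

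A separate simulation with the likelihood-ratio test (3,000 runs per case) agrees. Power goes from about 82–83% to 82–89% with one count and to 82–94% with both, with a loss under 1 point when the counts are not prognostic.

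**4. Type I error.** With 35% in both arms, the adjusted Wald test rejects in 4.2% to 5.0% of runs and the likelihood-ratio test in about 5% to 6%.

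**5. The screen.** If the counts are read as eligible and passed through a screen like that in 10.3, power is almost the same as with pre-specification: 84.2% against 84.4% at OR 1.5, and 87.9% against 88.0% at OR 2.0. Its type I error was 4.2% to 5.0%. When neither count is prognostic, the screen still admits at least one in about 26% of runs. For power, then, the restriction to demographic variables matters more than the significance test.

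**6. Change of target.** The marginal odds ratio is (0.5/0.5)/(0.2/0.8) = 4.0. Adjusting for one count with OR 2.0 or 3.0 per SD makes the conditional odds ratio 4.58 or 5.46, although the arm rates are unchanged.

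**The case against.** The strongest case against is that nothing in the documents shows entry counts to be prognostic. Treatment-emergent cytopenias causing most reductions does not mean baseline counts predict them. The nearest reported variable, history of neutropenia or thrombocytopenia, was not significant in a regression that covered 353 patients. Eligibility limits narrow the range of counts. Table 2 in 5.5.3 lets G-CSF replace a reduction for isolated neutropenia, and it lists many non-haematological triggers that counts do not bear on. All of this stands, and it is why the gain is a range that starts at zero. A history item is not a count at entry, however, so the earlier regression weakens the case without refuting it. Table 2 states no G-CSF option for thrombocytopenia, and the Day 1 rule in 5.5.2 states none.

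A reader might infer more than the documents support:

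- *That the counts are barred.* The term is undefined and nothing prohibits them. They simply have no stated route in.
- *That any fall below the floor in a patient entering at the ANC limit must produce a primary event.* The Day 1 reduction rule concerns newly met toxicity, and the documents do not say how many such patients to expect.
- *That chance imbalance in counts biases the comparison.* Randomisation and the test's error rate already allow for it.

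Two limits of the check also stand. The comparator is an unadjusted test, whereas 10.3 may admit some demographic covariates, possibly age. Age itself was not simulated.

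**Conclusion.** The point holds as a missed improvement, not as an error in the power calculation. A reader might infer that the plan loses power by leaving the counts out. It does not, because 81.6% was computed without covariates and reproduces.

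The possible gain is about 0 to 6 or 7 points with one count and about 0 to 11 or 12 points with both. These ranges rest on the 10.5 rates, an assumed OR per SD of 1 to 3 for each count and an assumed correlation of 0.3. Where in the range the trial would fall cannot be determined from the documents. The downside is under 1 point if the counts carry no information.

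The case for dropping the screen rests on pre-specification. A primary model should not depend on the reading of an undefined term or on groups formed partly by the outcome. The simulations do not show that the screen inflates type I error or costs power for these two variables.

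**What to change.** In 10.3, replace the significance screen with a short fixed list for the primary logistic model and the Cox model: age (continuous), and the last ANC and last platelet count before the first lenalidomide dose (both log scale, continuous). Age belongs on the list as the one predictor that Section 3.3 supports. Baseline comparisons can stay as description but should no longer select covariates.

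State that the adjusted odds ratio is conditional on these covariates, and report the unadjusted proportion with any reduction in each arm and their difference beside it.

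**Cost.** A short SAP edit, no new data and no change to any clinical rule. It uses three degrees of freedom. At the 10.5 rates, 40 × 0.50 + 40 × 0.20 = 28 events are expected, or 28/4 = 7 per coefficient for arm plus three covariates, which is a reason to keep the list this short. If none of the three is prognostic, expect a small power loss. It was under 1 point with two uninformative counts, and the three-covariate model was not simulated.
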